13.1 General Analytic Approach

Aim 1: Descriptive statistics will be used to summarize cross sectional survey results as well as baseline demographic and other exposure variables. Linear regression models or generalized linear regression models GLM with robust standard errors will be used to assess the association between variables of interest.

Aim 2: The primary analysis will compare the effectiveness of the two interventions (CC+ and CC) delivered to two populations (patients and providers/staff), potential confounding, effect modification, and mediation will be handled through study design (e.g. use of randomization to assign individuals to interventions), and statistically through stratification (population). Other published studies related to Caring Contacts have shown that patient-centered outcomes such as suicidal ideation change over a 6-month period in response to receipt of these interventions.⁵¹

Analyses will be stratified for patients and providers/staff, modeling the effects of intervention separately in these population groups. There is very little evidence regarding the effect of Caring Contacts on healthcare workers, and we hypothesize that the magnitude of effect may differ by population group. Generating evidence of the effectiveness of Caring Contacts with and without an introductory phone call in healthcare workers is the primary goal of this heterogeneity of treatment effect (HTE) analysis. **Linear regression with robust standard errors will be used to determine whether the primary outcome differs between CC+ vs CC.**

Linear regression and GLM models will be used in the analysis of the secondary outcomes. Robust/sandwich standard errors will be used to allow for departures of the observed standard errors from classic model assumptions.

All data analyses will be completed using appropriate statistical software (such as R and R Studio, SPSS, Stata, SAS, Python, and/or Microsoft Excel). Statistical significance will be determined based on a type I error (alpha) of 0.05 (two-sided). Confidence intervals will be reported in addition to p-values.

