Missing data will be tracked and prevented to the extent possible through participant retention measures. When missing data are unavoidable, they will be addressed through statistical analysis. With proper inclusion of variables associated with the probability of missingness, we will assess the nature of missingness; if the missing data follow a 'missing at random' framework, we will use multiple imputation.¹¹³ The most appropriate multiple imputation technique will be determined based on the distributions of missing data and observed variables.¹¹⁴⁻¹¹⁶ Multiple imputation methods incorporate the uncertainty of value estimation into parameter estimates. We will assess the sensitivity of estimates to the imputation approach and variables used in the imputation algorithm.

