5 ANALYSIS SETS/POPULATIONS/SUBGROUPS

We plan to survey up to 4,000 participants to address Aim 1. The total sample size for the Aim 2 trial is 660 participants, selected as a subset of those who complete the Aim 1 survey. For each stratum (patients, providers/staff), a sample of 330 participants (165 in each arm) allows 80% power to detect a difference of 5 units in the primary outcome (loneliness) if a minimum of 70% of participants are retained through study completion.

5.1 Inclusion & Exclusion Criteria: Aim 1

Provider & Employee Inclusion Criteria

- Provider or Employee at St. Luke's Health System
- Adults ≥ 18 years of age
- Proficient in spoken and written English language

Provider & Employee Exclusion Criteria

- Individuals who are unable or unwilling to provide informed consent to participate
- Individuals who are study staff for this study or the SPARC Trial
- Individuals who are participants in the SPARC Trial

Patient Inclusion Criteria

- Patient at a SLHS ED or primary care study site
- Current MyChart account user
- Adults ≥ 18 years of age
- Minors 12-17 years of age
- Proficient in spoken and written English language

Patient Exclusion Criteria

- Individuals who are unable or unwilling to provide informed consent to participate.
- Individuals who are participants in the SPARC Trial

5.2 Inclusion & Exclusion Criteria: Aim 2

Provider & Employee Inclusion Criteria

- Moderate or high score for loneliness, suicide ideation, psychological stress, anxiety, or depression:
 - NIH Toolkit Loneliness raw score of 13 or greater; or
 - C-SSRS score of 3 or greater; or
 - NIH Toolkit Perceived Stress raw score of 31 or greater for adults; or
 - GAD7 score of 11 or greater; or
 - PHQ9 score of 10 or greater
- Access to a phone for the duration of the study with the ability to receive text messages and phone calls

Provider & Employee Exclusion Criteria

- Individuals who are unable or unwilling to provide informed consent to participate
- Individuals who are study staff for this study or the SPARC Trial

Patient Inclusion Criteria

- Moderate or high score for loneliness, suicide ideation, psychological stress, anxiety, or depression:
 - NIH Toolkit Loneliness raw score of 13 or greater for adults and 16 or greater for adolescents; or

- C-SSRS score of 3 or greater; or
- NIH Toolkit Perceived Stress raw score of 31 or greater for adults or greater than 33 for adolescents; or
- GAD7 score of 11 or greater; or
- PHQ9 score of 10 or greater

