5.4 Subgroups

We plan to generate different effect estimates for (1) providers and staff, and (2) patients and are statistically powered to do so. We also plan to produce separate effect estimates for the following subgroups: adult vs adolescent patients, types of providers, low baseline C-SSRS score vs moderate to high baseline C-SSRS score, Hispanic vs non-Hispanic, female vs male, cisgender vs transgender or gender-nonconforming, heterosexual vs. homosexual, bisexual, or other; and urban vs rural; however, this study has not been specifically powered to identify differing treatment effects in each of these subgroups.

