6.2 Secondary endpoints

- Secondary outcomes include suicide ideation; suicidal ideation and behavior will be measured as score at 6 months using the Columbia Suicide Severity Rating Scale (C-SSRS). Scores range from 0-6. Risk factors for suicide will be measured by the Interpersonal Needs Questionnaire (INQ-15). This survey measures feelings of perceived burdensomeness and thwarted belongingness; scores range from 15 to 105. The changes from baseline thwarted belongingness and perceived burdensomeness scales will be analyzed separately.
- Depression will be measured as score at 6 months in the Patient Health Questionnaire-9 (PHQ-9); this questionnaire results in a score between 0-27, with higher scores indicating worse depression. A score of 5-9 is considered minimal depression, 10-14 is considered mild major, 15-19 is moderate major, and ≥ 20 is severe major. Analysis will be based on the continuous score, with categories examined in exploratory/sensitivity analysis.

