7.2.3 Subgroups

The primary outcome will be summarized in subgroups defined by:

- Age category: older adult (50+) vs. adult (26-49) vs younger adult (18-25) vs adolescent patients (<18),
- types of providers (patient-facing providers [physicians and APP; pharmacy, PAS, lab, specialists, technicians, MAs;; nursing; social support services] vs. non-clinical [office work and educators; senior management; and other]),
- baseline suicide risk (low baseline C-SSRS score vs moderate to high baseline C-SSRS score),
- Hispanic vs non-Hispanic,
- female vs male sex at birth,
- cisgender vs transgender or gender-nonconforming,
- heterosexual vs. homosexual, bisexual, or other, and
- urban vs rural.

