7.3 HANDLING OF MISSING DATA

Hot deck imputation will be used to account for missing 6-month outcomes. The 6-month outcomes will be sampled from complete cases on the same treatment arm, baseline loneliness score tertile, and study population. This method avoids making parametric

assumptions about the outcome distribution and preserves the relationship between measures (Andridge and Little (2010)). Twenty complete data sets will be imputed and Rubin's rule will be used to pool the results (Rubin 10987).

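### Hot-deck cells in SAP 7.3 omit the subgroup variables and each scale's own baseline, so subgroup differences estimated on the imputed data shrink by roughly the missing fraction and change scores gain noise

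*SAP*

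**What the plan says.** SAP 7.3 handles missing 6-month outcomes by hot deck. The donor rule is "The 6-month outcomes will be sampled from complete cases on the same treatment arm, baseline loneliness score tertile, and study population". Twenty completed data sets are pooled by Rubin's rule. The section gives as reasons that no parametric outcome distribution is assumed and that relations between measures are kept.

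The analyses that may draw on these data need more than the cells contain:

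- SAP 5.4: "We also plan to produce separate effect estimates for the following subgroups". The list covers age, provider type, baseline C-SSRS risk, ethnicity, sex, gender identity, sexuality and urban/rural residence. SAP 7.2.3 repeats it with more detail under "The primary outcome will be summarized in subgroups defined by". None of these is a cell variable.
- SAP 6.2, on the INQ: "The changes from baseline thwarted belongingness and perceived burdensomeness scales will be analyzed separately". SAP 6.3 treats stress as change from baseline too. Neither baseline enters the cells.
- SAP 7.2.1 adjusts the primary model for the baseline loneliness score, while the imputation uses three bands of it. This is also the only analysis section that names multiple imputation. Sections 7.2.2 and 7.2.3 are silent.
- SAP 5.3 evaluates primary and secondary endpoints in the intention-to-treat population.

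Protocol 13.4 describes the missing-data work as proceeding "With proper inclusion of variables associated with the probability of missingness" and promises to examine sensitivity to the imputation approach and its variables. SAP 7.4 limits sensitivity work to the primary results, when more than 10% of outcomes are missing.

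**The concern.** An imputation should carry at least the variables that the later analysis uses. Here a patient aged under 18 with a missing score receives the score of any completer in the same arm, loneliness tertile and population, and that completer may well be an adult. After imputation, part of each subgroup consists of people who respond like the average of the arm. The subgroup effects then move toward each other, and a real difference, such as adolescent versus adult, is understated.

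Similarly, a participant with a high baseline INQ score receives a 6-month INQ score chosen without regard to it, and the change score then subtracts a baseline that had almost no part in producing the imputed value. At stake are the credibility of the subgroup estimates and the precision of the change-score outcomes.

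**Working it through.** **Inputs from the documents.** 330 per population and 165 per arm (SAP 5); at least 70% retained, so up to 30% missing (SAP 5); two-sided alpha 0.05 (Protocol 13.1); cells of arm × tertile × population (SAP 7.3).

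**The plan's own figure.** SAP 5 claims 80% power for 5 units. With 165 × 0.7 = 115.5 completers per arm, the implied SD is 5 / [(1.96 + 0.842) × √(2/115.5)] = 13.6. No SD is stated, so the claim can only be solved backwards. Only the retention figure is needed below.

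**Cells.** 2 × 3 × 2 = 12 cells, with 115.5 / 3 ≈ 38 donors each.

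**Subgroup effects.** Let subgroups 1 and 2 have effects δ1 and δ2, missing fractions m1 and m2, and respondent shares w1 and w2. Assume the subgroup is unrelated to tertile and missingness is random within subgroup and cell. A missing row carries the average effect w1δ1 + w2δ2, so after imputation

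effect in subgroup k = (1 − mk)δk + mk(w1δ1 + w2δ2).

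Subtracting, the difference δ1 − δ2 is multiplied by 1 − m1w2 − m2w1. With equal missingness this is 1 − m, whatever the SD or correlations.

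- 30% missing, effects 5 and 0, subgroup share 30% (average effect 1.5): 0.7 × 5 + 0.3 × 1.5 = 3.95 and 0.3 × 1.5 = 0.45, a difference of 3.5 in place of 5.
- Simulation of 500,000 records gave 4.43, 3.99 and 3.43 at 10%, 20% and 30% missing (formula 4.5, 4.0, 3.5). Complete cases gave 4.93 to 5.03. The overall effect of 1.5 was recovered (1.48 to 1.54).
- By the same formula, 15% missing leaves 85% of the difference.
- Subgroup correlated 0.4 with baseline loneliness, 30% missing: 3.65 remained, a 27% loss.
- 40% versus 20% missing in equal groups: w1 = 0.30/0.70 = 0.429, factor 1 − 0.4 × 0.571 − 0.2 × 0.429 = 0.69.
- 50% missing in a 20% subgroup versus 25% elsewhere: w1 = 0.10/0.70 = 0.143, factor 1 − 0.5 × 0.857 − 0.25 × 0.143 = 0.54, a 46% loss.

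**At trial size** (330, 30% missing, assumed SD 10 and baseline correlation 0.6, true difference 5), the mean estimate was 3.45 against 4.96 in complete cases, and interaction power was 32% against 65%. Interval coverage stayed near 95% because the Rubin SE (2.12) exceeds the empirical SD (1.55).

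**Secondary scores.** Assumed correlations: own baseline to 6 months 0.60; own baseline with baseline loneliness 0.5; baseline loneliness to the 6-month secondary score 0.4. The only route from own baseline to an imputed value is the tertile, which holds about 0.79 of the variance of a normal score (outer-tertile mean 1.09; 2/3 × 1.09² = 0.79).

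- Correlation in imputed rows: 0.5 × 0.4 × 0.79 = 0.16 (simulated 0.16), against 0.60.
- SD of change for a scale with SD 5: √(50 − 50 × 0.16) = 6.5, against √(50 − 50 × 0.60) = 4.5.
- Pooled slope on own baseline at 30% missing: 0.7 × 0.60 + 0.3 × 0.16 = 0.47.
- Arm effect, true −1.0: −0.99 when drop-out tracks own baseline equally in both arms; −1.39 when it does so in CC+ only (baseline-adjusted complete cases −0.98).
- Correlation between 6-month measures: 0.50 observed and 0.50 imputed, if one donor supplies the whole record.

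**The case against.** The strongest reply is that the premise is inferred. Multiple imputation is named only for the primary analysis, and SAP 7.2.3 speaks of summarizing the outcome in subgroups. Complete-case subgroup estimates would not shrink. This stands as a condition on the point. But 7.3 covers 6-month outcomes in general and 5.3 places the secondary endpoints in the intention-to-treat set, so the inference is reasonable and the SAP should settle it.

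Thirty percent missing is the planning limit, and the loss is smaller with better retention. The contrast the documents call powered, estimates for patients and for providers/staff, is safe because population is a cell variable. The other subgroups are declared not specifically powered. That lowers the stakes, but low power does not justify a systematic pull toward no difference.

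SAP 7.3's remark about keeping relations between measures can fairly be read as concerning 6-month measures drawn together, and under a single donor that is true. For loneliness itself the baseline link is coarsened, not lost: 0.6 × 0.79 ≈ 0.48 against 0.60.

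A reader might infer that drop-out related to baseline depression biases the primary arm contrast. That does not follow from the plan. In simulation, such drop-out in both arms gave bias of at most 0.004 SD. In CC+ only it gave −0.046 to −0.068 SD, but complete-case regression adjusted for baseline loneliness gave −0.026 to −0.053, so most of it comes from leaving depression out altogether. SAP 7.4 also plans arm-specific missingness scenarios and a tipping-point analysis for the primary results.

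Protocol 13.4's promise to vary the imputation variables stands, but the SAP does not carry it to subgroups or secondary scales.

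**Conclusion.** The point holds, conditionally on imputed data being used in 7.2.2 and 7.2.3. Differences in effect between subgroups then shrink by roughly the missing fraction: about 30% at 30% missing, about 15% at 15%. The factor is exact only with equal missingness and a subgroup unrelated to loneliness tertile; in the other cases tried, at 30% missing overall, the loss ran from 27% to 46%. It does not depend on the assumed SD or correlations, whereas the power figures do.

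For secondary scores the own-baseline link falls to about 0.16 from an assumed 0.60. The effect is chiefly noise in the INQ and stress change scores. The arm contrast is biased only if drop-out tracks that baseline differently by arm.

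It would go too far to conclude that the primary result is compromised. Its SE rises by only 2% to 3% against complete-case regression, and the overall effect is recovered. This is a worthwhile correction to supporting analyses.

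**What to change.** In SAP 7.3, replace the tertile cells with chained-equation predictive mean matching, run within arm and population. Predictors should be baseline loneliness as a continuous score, the own baseline of each scale being imputed, and the 7.2.3 subgroup variables with sparse levels collapsed. Keep 20 or more data sets and Rubin's rules. Running within arm is what lets a subgroup-specific effect enter the imputation. Values still come from observed donors, so the aim of avoiding a parametric distribution is kept.

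Crossing the subgroups into the existing cells is not workable: of about 38 donors, a 20% subgroup leaves about 8. Matching within arm and population has about 115 donors. In a simulation with 330 per population, 30% missing, SD 10 and correlation 0.6, a true gap of 6.0 became 4.1 to 4.2 under the hot deck and 5.8 to 5.9 under predictive mean matching.

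State in 7.2.2 and 7.2.3 that these imputed data are used. If complete cases with baseline adjustment are intended for subgroups, state that.

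The cost is SAP wording and routine programming, since the variables are already collected. There are two drawbacks. Sparse levels must be collapsed. Scale-by-scale matching also no longer takes a whole record from one donor, so the other 6-month scores should be predictors in the chained equations.

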7.4 SENSITIVITY ANALYSIS

If the proportion of missing 6-month outcomes is greater than 10%, we will assess the sensitivity of the primary results to a variety of possible missingness generating models (Cro et al. 2020). Sensitivity analyses will explore the possibilities that missing data is more likely to reflect poor outcomes or the missing data mechanism varies by treatment arm. A tipping point analysis will be included.

